### ***Isoflurane Blocks Neurotransmitter Release in PC12 Cells: Forskolin, Theophylline and Caffeine Reverse this Block***

Anesthetics modulate the activity of various channels and receptors, thereby altering neurotransmitter release. For this experiment, PC12 cells were permeabilized with digitonin, and then cells were stimulated by exposing them to  $Ca^{2+}$ . Permeabilization disrupts the cell's resting potential and equilibrates the intracellular and extracellular  $Ca^{2+}$  levels. Under these conditions, modulation of channels or receptors should have no effect on neurotransmitter release. In earlier studies, PC12 cells were also dialyzed with known  $Ca^{2+}$  concentrations, via a patch pipette from a constant holding potential of -65 mV; these studies validated the digitonin methodology. Exocytosis was elicited in the presence and absence of isoflurane (0.5 mM). Basal ( $Ca^{2+}$ -independent) neurotransmitter release is virtually non-existent in digitonin permeabilized PC12 cells in  $Ca^{2+}$ -free conditions, but

[figure not shown]

Fig. 1 – Forskolin, theophylline and caffeine reversed the inhibition of neurotransmitter release produced by isoflurane. PC12 cells were permeabilized with digitonin (20  $\mu$ M) and then stimulated by exposing cells to a solution containing 100  $\mu$ M  $Ca^{2+}$ . Neurotransmitter release was monitored with an amperometric electrode which gently touched the cell. Under these conditions, isoflurane (0.5 mM) significantly inhibited neurotransmitter release by ~36% ( $p < 0.05$ , relative to control and all other conditions). The number of events recorded from control PC12 cells were about the same as those from PC12 cells exposed to isoflurane + forskolin (5  $\mu$ M) or isoflurane and theophylline (50  $\mu$ M) or isoflurane and caffeine (50  $\mu$ M) (Control  $81.28 \pm 5.1$  (n=36), isoflurane  $52.29 \pm 6.31$  (n=17), isoflurane + forskolin  $83.4 \pm 6.1$  (n=17), isoflurane + theophylline  $79.75 \pm 7.07$  (n=12), isoflurane + caffeine  $79.43 \pm 12.12$  (n=7) events per stimulation).

robust release is observed upon exposing cells to  $Ca^{2+}$ -containing solutions. Physiologically, release is evoked by the activation of voltage-gated  $Ca^{2+}$  channels. The proximity of  $Ca^{2+}$  channels to synaptic release sites suggests that  $[Ca^{2+}]_i$  may rise to levels above 100  $\mu$ M at the vesicle. To mimic these levels in our experiments, evoked neurotransmitter release was elicited by exposing digitonin-permeabilized cells to 100  $\mu$ M  $Ca^{2+}$ , for 2 min, in the absence or presence of isoflurane.

In previous studies we have shown that 0.5 mM (~1.5 MAC) isoflurane inhibits neurotransmitter release by ~39% (Herring *et al.*, 2009; Herring *et al.*, 2011). Fig 1 shows that isoflurane (0.5 mM) significantly inhibited neurotransmitter release by ~36% ( $p < .05$ ) in this study.

Three drugs that elevate intracellular cAMP were then tested for their ability to reverse the inhibition produced by isoflurane. Fig. 1 shows that all three drugs, forskolin (5  $\mu$ M) or theophylline (50  $\mu$ M) or caffeine (50  $\mu$ M), reversed the isoflurane-mediated inhibition of neurotransmitter release.

### Caffeine Accelerates Recovery from Isoflurane Anesthesia

[figure not shown]

Fig. 2 - Caffeine accelerated recovery from isoflurane anesthesia. A, Adult rats were anesthetized as described. Five minutes prior to discontinuing the isoflurane the animals received an intravenous injection of either saline (control ■) or saline with 25 mg/kg caffeine (●). The isoflurane was terminated and the animals were allowed to recover. B, Average waking time normalized to the Control value, set to 100%, at different caffeine concentrations (n=13; control, n=8; 0.1 mg/kg, n=13; 1 mg/kg, n=12; 5 mg/kg, n=12; 25 mg/kg). Inset plots the percent reduction in waking time as a function of the caffeine concentration. The midpoint was at ~0.9 mg/ kg caffeine and the maximal reduction of waking time was ~60.5%.

with caffeine (●), 25 mg/kg, 5 minutes prior to discontinuing the isoflurane. Caffeine dramatically sped recovery from anesthesia. Fig. 2B shows the average recovery time at

The results in Fig. 1 suggest that elevating intracellular cAMP reverses the inhibition of neurotransmitter release produced by isoflurane *in vitro*. Does elevating cAMP alter recovery from anesthesia in animals? To address this question, we examined emergence from anesthesia in rats. First, we assessed waking from anesthesia in the absence of any other drug to assess population variability. Rats, weighing 420-510 gm, were placed in an anesthetizing apparatus consisting of a gas-tight box where they were exposed to 3% isoflurane (in 3 L/min O2) for 8 minutes. Isoflurane levels were then decreased to 2% (in 2L/ min O2) for an additional 45 minutes. The rats were then removed from the anesthetizing chamber and placed on their backs in the middle of a large table. Recovery time from anesthesia for rats is defined as the time from when the animals are removed from the anesthetizing chamber to when they stand upright with 4 paws on the table. Caffeine elevates intracellular cAMP by inhibiting phosphodiesterase. Caffeine is of particular practical interest as it is such a widely used and largely innocuous drug. Fig. 2A shows a graph of recovery times from isoflurane anesthesia for control rats (■) or for animals injected

different concentrations of caffeine. The inset shows a plot of the dose response curve fit to the data showing that the midpoint occurs at approximately 0.9 mg/kg. Of note, an average person consumes more than 0.9 mg/ kg of caffeine in a cup of coffee.

**Methods:** Adult rats were anesthetized with 3% isoflurane for 8 minutes and were then exposed to 2% isoflurane for 45 minutes. During the anesthesia an I-V was inserted into a tail vein, while anesthesia was maintained with a nose cone. Five minutes prior to discontinuing the anesthetic the animals received an I-V injection of either saline (control, ■) or saline with drug (●). The anesthetic was then terminated and the animals were allowed to wake up breathing room air. The rats were placed on their backs on a table. Waking time was defined as the time between terminating the anesthetic and the rats were standing with 4 paws on the table.

### ***Caffeine Does not Alter Heart Rate, Blood Pressure or Breathing Rate***

[figure not shown]

Fig. 3 plots vital signs immediately before or 10 minutes after injection of caffeine in isoflurane anesthetized rats. Anesthetic conditions were similar to those in figure 2. No significant changes in heart rate, blood pressure (BP) or breathing rate (BR) were observed as a result of caffeine application (25 mg/kg). In all cases O2 blood saturation was at either 99% or 100%.

Fig. 3 - No significant change in blood pressure, heart rate or respiratory rate in rats exposed to drug. Rats were anesthetized as described in Fig. 2. Drug, 25 mg/ kg, was injected into each animal. Just prior to drug injection blood pressure, heart rate and respiratory rate was measured with an IITC Life science Multi Channel Blood Pressure system, using a tail cuff. 10 minutes after drug, the parameters were re-measured. HR= Heart Rate, BR = Breathing Rate. Pre = Pre drug application. Post = 10 minutes after drug application.

### ***Caffeine Accelerates Recovery from Propofol Anesthesia***

Fig. 4 plots recovery times from propofol anesthesia from control rats (■) or from rats injected with 25 mg/kg of the drug (●). Adult rats were anesthetized in the following manner. Rats were placed in a gas tight anesthesia box where they were exposed to 3% isoflurane for 8 minutes. IVs were inserted into a tail vein and the rats were allowed to wake. The rats then received a bolus inject of propofol (4 mg/kg) and either saline (Control) or drug in saline (25 mg/Kg). The rats were placed on their backs on a table

[figure not shown]

Fig. 4 - Drug accelerates recovery from propofol anesthesia. Adult rats were anesthetized with 3% isoflurane for 8 minutes at which time an I-V was inserted. The animals were allowed to wake and then a bolus of propofol (4 mg/ kg) was injected along with either saline (Control, black squares) or with 25 mg/kg drug in saline (red circles). The animals were allowed to wake. The same animals were used as controls and to test drug (n=16 per group).

and allowed to wake with room air. As before, waking was defined as 4 paws on the table. Note that the caffeine was applied at the same time as the propofol which may not have been optimal.

This last result opens the possibility that caffeine accelerates recovery from anesthesia for all anesthetics.

#### 1.1.4 Clinical Data to Date

##### Work Done By Others:

There are two clinical trials that have tested caffeine in anesthetized patients. Both trials were carefully vetted. In a recent clinical trial in anesthetized children, caffeine was found to be safe (the trial was to determine whether caffeine could reduce the number of children who experience adverse post-extubation respiratory events (Khalil *et al.*, 2008) – caffeine helped significantly). Note that the concentration of

caffeine used in this study was quite high.

Caffeine has been shown safe to use in anesthetized adults. In a clinical trial, to determine whether caffeine ameliorated post anesthesia nausea and vomiting, patients were given 500 mg caffeine during anesthesia. This combination, anesthesia and caffeine, was found to be safe (Steinbrook *et al.*). Note that 500 mg in that trial is similar to the low end of the range that we propose for our trial.

#### Preliminary Data from Pilot Study:

[figure not shown]
[figure not shown]
[figure not shown]

### **1.1.5 Rationale for Conducting this Research**

Our lab has studied anesthetics for over fifteen years. We have spent considerable time studying the inhibition of neurotransmitter release produced by anesthetics (Herring *et al.*, 2009; Herring *et al.*, 2011; [name] *et al.*, 2012; [name] *et al.*, 2013). We thought that if we could reverse this action that we would be able to reverse aspects of anesthesia. Several drugs were studied; these drugs normally facilitate neurotransmitter release. If inhibiting neurotransmitter release causes anesthesia then drugs that facilitate neurotransmitter release should aid in reversing anesthesia. Elevating intracellular cAMP, with drugs like caffeine, is well known to facilitate neurotransmitter release. We found that drugs that elevate intracellular cAMP levels caused rats to wake up very quickly from anesthesia.

A variety of drugs are used during general anesthesia that are reversed pharmacologically afterwards. For example opioid drugs, frequently used to suppress pain, can be reversed pharmacologically following surgery. Other drugs like anticoagulants and muscle relaxants are used in a similar manner. General anesthetics induce a coma-like state; unfortunately recovery from anesthesia induced loss of consciousness cannot be reversed (Solt *et al.*, 2011). Recovery is passive and is due to the

discontinuation of anesthetic. Problematically, recovery is somewhat random, dependent upon a variety of genetic, age, physical condition and gender related factors that are beyond the clinician's control (Solt *et al.*, 2011; Chemali *et al.*, 2012; Taylor *et al.*). Cognitive impairments persist for hours following anesthesia. Outpatients are released from hospital after anesthesia/ surgery after an ever diminishing recovery period in order to constrain hospital costs. This is a recipe for increasing anesthesia-induced accidents. It would be extremely beneficial to be able to time recovery from anesthesia in a reproducible manner and to have that recovery be complete. Anesthesia in rodents is thought to be very similar to that in humans (Thurman *et al.*, 2008). We have tested a variety of drugs in rats and we have identified four different drugs that appear to wake animals rapidly and reproducibly after terminating anesthesia. We have chosen one of the four drugs and would like to test it in humans. These studies have the potential to impact medicine in an important way and in a relatively short time frame.

### **1.1.6 Dose Rationale and Risks/Benefits**

The drug that will be used in this study is caffeine which is commonly consumed by millions of people daily. It is the most popular drug used worldwide found in more than 60 plants. It is classified by the FDA as "Generally Recognized as Safe". This was a critical consideration for our study. To be able to find a drug that would be considered safe. An IV formulation of caffeine is in clinical use, for treating apnea of prematurity in neonates. The dosages of caffeine in this study are within the range used for the above clinical conditions. For example, the recommended loading dosage for premature infants being treated for apnea of prematurity is 20 mg/ kg, a 33% higher dosage that we propose in adult male volunteers. The dosage that we have chosen is not associated with serious side effects ("caffeine has few unwanted side effects and is safe even in very large doses". This quote is from (Rang *et al.*, 2001) the most widely used pharmacology textbook in medical schools. We hypothesize that injection of caffeine at the end of anesthesia at clinically relevant dosages will facilitate the emergence of a subject from general anesthesia. Additionally, caffeine may improve cognitive function recovery after general anesthesia.

## **1.2. OBJECTIVES**

### **a) Hypothesis**

Anesthesia is thought to work similarly in humans and animals (Thurman *et al.*, 2008). In our preliminary studies we found that drugs that elevate intracellular cAMP, like forskolin or caffeine, dramatically accelerated recovery from anesthesia in rats. Caffeine appeared to have a similar effect in two human test subjects. We hypothesize that drugs that elevate intracellular cAMP will dramatically accelerate recovery from anesthesia in humans.

### **Objectives**

#### **Primary Objective**

To determine whether drugs that elevate cAMP levels accelerate recovery from anesthesia.

### **Secondary Objective(s)**

To determine whether drugs that elevate cAMP help ameliorate the cognitive problems that persist for hours following anesthesia.

## **2. STUDY DESIGN**

### **2.1 Type of Study**

This is a Randomized, Double-Blinded, Placebo Controlled Study.

### **2.2 Duration of Study**

Screening: 1 week

Intervention: 6 weeks total

Follow-up: 2 weeks

Part 1: We will enroll up to 8 test subjects in a full scale trial. The estimated duration of this trial will be approximately 16 weeks followed by a 2 week follow up period.

Week 1: Explanation of the trial and signature of informed consent form. Detailed medical exam and physical exam. Toxicology screen and acceptance into trial. Training with psychomotor tests.

Week 2: Volunteers will be exposed to isoflurane anesthesia as described below and then receive and injection of either a saline solution or caffeine citrate (both investigators and subjects will be blind to composition of injection). Psychomotor tests will be carried out. There will be a toxicology screen. Later that day and then the day after the session, there will be a telephone follow-up with the subject.

Week 3: There will be a telephone follow-up with both volunteers.

Week 4-6: Volunteers will be exposed to isoflurane anesthesia as described below and then receive and injection of either a saline solution or Caffeine (both investigators and subjects will be blind to composition of injection). Psychomotor tests will be carried out. There will be a toxicology screen. Later that day and then the day after the session, there will be a telephone follow-up with the subject.

Weeks 6: There will be telephone follow-ups with both volunteers.

Week 7: There will be a final series of telephone follow-up with both volunteers. If there are no issues identified, this will be the last contact with the volunteers.

We are suggesting that the trial take place over 16 weeks due to scheduling conflicts i.e. the possibility that subjects are not available. We hope to anesthetize 2 subjects per single lab day.

We are asking to be allowed to enroll up to 8 additional volunteers, but we will only require 6-8 to complete the study. If we need additional subjects due to dropout from the trial, we will ask the IRB for additional subjects. After 6 subjects are completed we will submit a continuing review after enrolling 6 additional subjects in order to inform the IRB of the study progress, how subjects tolerated the dosing changes, and if there were any subject safety issues.

If we are given IRB approval, the next set of test subjects will take 4-6 weeks to complete the trial. There will also be a two week follow-up period.

For the full trial, we are asking for extra time up to 26 weeks in the trial to allow for expected dropouts.

### **2.3 Schedule of Events**

Each subject will attend 3 sessions to complete the study. In the first session, an anesthesiologist will explain the purpose of the trial and carefully go over the consent form. If the subject is willing to enroll the consent form will be signed. Then the anesthesiologist will take a detailed medical history and perform a physical examination of the subject. A baseline EKG and urine toxicology screen text will be obtained. If the subject meets the criteria for the study, the subject will be enrolled in the trial. At this point a pre-study training session will be provided to familiarize the subject with the psychomotor tests. In the following two sessions, each subject will receive general anesthesia in one session (with a saline injection as a placebo control) and receive general anesthesia plus an injection containing caffeine citrate (15 mg/ kg) in the other session in a randomized manner. For each subject, each session involving anesthesia will be at least 2 weeks apart. Detailed study procedure will be described in section 5 below.

**Please Note:** We will try to process two subjects on a single anesthesia day. One at 7:00 AM and another at 1:00 PM. In the Pilot study we tested one subject per day. The subjects arrived at UC at 7:00 AM and the entire anesthesia procedure including recovery was finished by 11:00 AM. That was wasteful, in terms of time. Normally anesthesiologists put multiple people to sleep per day. They don't finish their days at 11:00 AM. That is why we would like to have one subject in the morning and a second subject in the afternoon.

### **2.4 Sequence and Duration of all Study Periods**

The total time of each study session, including the pre-anesthesia preparation, testing and recovery from anesthesia, will be ~4 hours.

### **2.5 Method for Assigning Subjects to Treatment Groups**

The University of Chicago Investigational Drug Service (IDS) will prepare the injectable solutions for our trial. They will provide us with either saline or with caffeine citrate, 15 mg/ kg. They will not inform the research team of their preparations. There is no way to identify whether caffeine is present in a solution by looking at the solution (caffeine citrate is colorless and odorless). The entire experiment will be done blind by the research team and by the volunteer. The only requirement will be that at the end of the test the

subject will receive one round of anesthesia without caffeine and one round with caffeine. The assignment of which drug to use will be carried out with a random number sequence generated by random.org.

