#### **5.2 Study sessions 2 – 3**

In the following two sessions, each subject will receive general anesthesia in one session (with a saline injection as a placebo control) and receive general anesthesia and caffeine citrate (15 mg/ kg equal to 7.5 mg/ kg of pure caffeine) in the other session in a randomized manner. For each subject, each session involving anesthesia will be at least 2 weeks apart.

For each session, subjects will be asked not to eat and drink 8 hours prior to the study in order to minimize the potential risk for aspiration during anesthesia. They will be asked to refrain from alcohol or drug use for 24 hours prior to the sessions. A toxicology screen will be used for each session. Once the subject is checked in, a peripheral intravenous catheter (IV) will be inserted on one of the arms by the anesthesiologist ([name], [name] or [name]). The IV is used to administer medications during the course of the study. After the IV insertion, American Society of Anesthesiologists (ASA) standard monitoring, including EKG, blood pressure (BP), respiratory rate, end tidal CO2, pulse

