**\*Please note:** We may recruit one or two additional anesthesiologists to our team. We will only recruit attending clinicians. They would take all the human clinical trial coursework and then we would have training sessions related to our protocol. The IRB should be aware that our protocol was designed to be as similar as possible to a standard surgical session with anesthesia, so that our research protocol will be instantly familiar to any experienced anesthesiologist.

Schema:

Procedure	Screening Session 1	Study Session 1	Study Session 2
Time	1 week prior to study	Start of Study: week 0	Week 2-4
Explain Trial to subject Obtain Consent	X		
Medical History	X		
Physical exam	X		
Vital signs	X	X	X
EKG	X	X	X
Urine Toxicology screen	X	X	X
Enroll Subject in Trial	X		
Psychomotor Training session	X		
Propofol Induction – Isoflurane maintenance		X	X
**Saline Control injection		X	
**caffeine (15 mg/ kg) injection			X
Psychomotor session 1 + 2		X	X
Adverse Event report		X	X

\*\*Please note that the drugs will be applied in a double-blind manner and will be prepared by a hospital pharmacist.

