## 6.2 Statistical Methods

We hope to use a simple paired t-test to analyze the data, using volunteers as their own controls.

Crossover study - Each volunteer receives anesthesia 2 times: once without drug (control) and once with caffeine (test). Our animal studies suggest that variance is dramatically minimized when test subjects can be used as their own controls, in this manner. If humans recapitulate the rodent studies then 8 volunteers should provide an adequately

sized sample to answer the research question. The study was originally divided into two parts. The first part, the Pilot study has been completed.

Part 1: In order to demonstrate feasibility and safety, we carried out a pilot study of 2 healthy human volunteers to assess whether caffeine aids these subjects in recovering from isoflurane anesthesia. Recovery times were measured in three ways: as the time between the time when anesthetic is terminated until the subject starts to gag, can open his eyes, and the subject is able to respond to simple commands (like squeeze the clinician's hand). Each of the three endpoints was monitored and plotted separately. In this pilot study caffeine citrate (caffeine) was used at 10 mg/kg. By comparing subjects that wake from anesthesia who are injected with a saline solution to subjects that are injected with caffeine we were able to show that caffeine is as efficient in humans as in rodents. Now that we have demonstrated safety and feasibility, if the IRB gives us permission, we will continue to Part 2 of our study. Time from the end of anesthesia to eye opening will be analyzed, as will be the time from the end of anesthesia to response to a simple command. Each parameter (gagging, eye opening and response to command) will be analyzed and plotted separately.

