### **6.3 Subject Population(s) for Analysis**

The data from all subjects will be analyzed without knowledge of whether the data comes from a control or test condition. After breaking the code, data will be grouped accordingly. All data will be analyzed in two different ways. Using a paired t-test data from subjects that have completed the two anesthesia sessions of the study will be analyzed and plotted. Separately, using an unpaired t-test all data will be grouped together including that from subjects who did not finish the trial. In this way the data will be compared. Only data from subjects that failed the toxicology screen will be excluded.

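### The schema shows one fixed treatment order that contradicts the randomised order in the text, and section 2.5 does not say whether the two orders are balanced across the 8 subjects

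*Combined protocol and SAP*

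**What the plan says.** Section 2.5 gives preparation of the injections to the pharmacy's Investigational Drug Service and says "The assignment of which drug to use will be carried out with a random number sequence generated by random.org". The single requirement it adds is within subject: by the end, the "subject will receive one round of anesthesia without caffeine and one round with caffeine". It gives no allocation ratio, block or number of subjects per order, and no other available section does so. Section 4.3A lists a randomisation schedule among the pharmacy's standard binder contents, without describing it.

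Several sections make the order random. Section 5.2 gives saline in one session and caffeine "in the other session in a randomized manner". Section 2.3 says the same, section 2.2 allows either injection at each anesthesia session, and section 9.1 has each volunteer's solution prepared at random.

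The schema at the end of section 5.2 differs. The row "Saline Control injection" is marked under Study Session 1 only, and the row "caffeine (15 mg/ kg) injection" under Study Session 2 only. The footnote to both rows reads "Please note that the drugs will be applied in a double-blind manner". It does not say that the order shown is an example.

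On analysis, section 6.2 says "We hope to use a simple paired t-test to analyze the data, using volunteers as their own controls", and section 6.3 says "Using a paired t-test data from subjects that have completed the two anesthesia sessions of the study will be analyzed and plotted". Neither mentions a period or sequence term.

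**The concern.** In a two-session crossover, anything that changes between the first and second session is a period effect. Familiarity with the procedure and practice on the tests are examples. Equal numbers in each order cancel a period effect from the mean paired difference. Unequal numbers leave part of it in, and a single order leaves all of it in.

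The schema as printed is that last case. If it were followed, no later analysis could separate caffeine from session number, and the session number would reveal the treatment. Section 4.3A says the pharmacy reviews the protocol before preparing drug, so a contrary table should not stay in it.

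The missing statement on balance is a smaller matter, but chance imbalance has most effect in small trials. This one plans up to 8 subjects, needs 6–8 completers (section 2.2) and expects considerable dropout (section 3.13).

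**Working it through.** **Schema against text.** Sections 2.2, 2.3, 2.5, 5.2 and 9.1 all describe a random order, or either injection at each session. The schema shows saline then caffeine for everyone. Both cannot be right, and the double-blind footnote fits only the random order.

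**Inputs for the balance question.** The plan gives no figure on balance, so there is none to reproduce.
- From the documents: 8 subjects (section 3.1); the 0.01 level and the rat results of section 6.1 (540 s, SD 159.04, on saline; 269.67 s, SD 103.69, on caffeine), a difference of 270.33 s.
- Assumed, because the documents are silent: an independent 1:1 draw per subject, a two-sided test, within-subject correlation 0.5, and a period effect of 30, 60 or 120 s.

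**Step 1: chance of each split.** P(k of 8 in one order) = C(8,k)/2^8. The share of the period effect π left in the unadjusted paired mean is (n1−n2)/n.

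| Split | Probability | Share of π carried |
|---|---|---|
| 4:4 | 70/256 = 27.3% | 0 |
| 5:3 | 112/256 = 43.8% | 25% |
| 6:2 | 56/256 = 21.9% | 50% |
| 7:1 | 16/256 = 6.3% | 75% |
| 8:0 | 2/256 = 0.8% | 100% |

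With 6 subjects, 3:3 occurs in 20/64 = 31.3% of draws. With 7, exact balance is impossible.

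**Step 2: SD of paired differences.** √(159.04² + 103.69² − 2·0.5·159.04·103.69) = 139.8 s.

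**Step 3: type I error of the planned paired t-test** (simulated, n = 8, nominal 1%).

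| Split | π = 30 s | 60 s | 120 s |
|---|---|---|---|
| 4:4 | 0.89% | 0.61% | 0.14% |
| 5:3 | 0.97% | 0.80% | 0.35% |
| 6:2 | 1.12% | 1.37% | 1.53% |
| 7:1 | 1.41% | 2.67% | 6.67% |
| Averaged over independent draws | 1.02% | 1.03% | 1.14% |

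The test is conservative at 4:4 and 5:3, which together make up 182/256 = 71.1% of draws. With 6 subjects the average is 1.00–1.18%. The schema's single order with 8 subjects would give 1.9%, 5.3% and 24%.

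**Step 4: power of the planned test for 270 s.** At π = 0, 30, 60 and 120 s, simulated power averaged over independent draws is 93.6, 92.4, 88.7 and 71.6%. At a fixed 4:4 it is 93.5, 92.5, 89.2 and 71.9%. The gap is at most 0.5 points.

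**Step 5: precision of the estimate.** At 4:4 the standard error is 139.8/√8 = 49.4 s. Under independent draws (n1−n2)/n has mean 0 and variance 1/8, so the root mean squared error is √(139.8²/8 + π²/8). At π = 60 s this is √(2443 + 450) = 53.8 s, or about 54 s against 49 s.

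**Step 6: power of a period-adjusted check** (not in the plan). SE = SD·√(1/n1 + 1/n2)/2, with n−2 degrees of freedom. Power for 270 s is 90.4% at 4:4, 88.3% at 5:3, 79.4% at 6:2 and 52.5% at 7:1. Averaged over independent draws, with 8:0 counted as zero, it is 84.0%.

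**The case against.** The strongest objection is that balance hardly affects the planned analysis. Independent random ordering is valid: averaged over draws, the paired t-test keeps its error rate and loses at most about half a point of power. The fall from 90% to 84% belongs to a test that the plan does not contain. All of this stands.

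The 27% is also conditional. A random.org sequence is compatible with a balanced list, the pharmacy may hold one, and some text following section 4.3A was not available for this review. A reader might infer that the plan tosses a coin for each subject, but the documents do not say so.

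The period effect has no source in the documents. Training before the first anesthesia session, new symbol codes each time, a gap of at least 2 weeks and standardised anesthesia all limit it. For eye opening it may be small; practice matters mainly for the psychomotor secondary endpoints.

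A reader might also infer from the schema that the order is fixed. Five sections and the footnote speak against that, and section 4.3A provides for a protocol-specific procedure sheet and for checking each order. The single-order error rates above therefore describe a trial that the text does not plan.

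What survives is that the table is wrong as printed, and that section 2.5 leaves a choice unstated that costs almost nothing to settle.

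**Conclusion.** The point holds as one correction and one low-cost improvement. The schema contradicts the randomised order and must be reconciled with it; this rests on no assumption. Balance of order is not documented in the available text. If orders are drawn independently and all 8 subjects complete, an uneven split has probability 1 − 0.273 = 0.727, and a 5:3 or 6:2 split leaves 25% or 50% of any period effect in the estimate.

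The documents do not support the stronger reading that the primary test is flawed or its error rate inflated. Average type I error is about 1.0–1.2% under the assumed 30–120 s effects, correlation 0.5 and rat SDs. Balance makes the realised estimate more precise (about 49 s against 54 s at an assumed 60 s effect) and makes a period-adjusted check efficient.

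**What to change.** 1. In the schema, mark both study sessions as saline or caffeine according to the randomisation.
2. In section 2.5, state that the pharmacy allocates the two orders in equal numbers (as near as possible if the total is odd) from a concealed list. If the list is already balanced, one sentence saying so is enough. Block details can stay in the pharmacy's schedule, since an emergency unblinding under section 8.6 reveals that subject's whole order.
3. In section 6.2, prespecify a period-adjusted two-sequence crossover analysis as a sensitivity analysis and keep the paired t-test primary. Making the adjusted test primary would cost power when there is no period effect: 93.6% to 90.4% at 4:4, and 72.0% to 60.1% at 3:3.

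The cost is slight pharmacy and analysis work and no extra subjects. Dropout can still unbalance the completers, but within limits. From 4:4, losing two subjects for reasons unrelated to order leaves 3:3 in 16/28 = 57% of cases and 4:2 in 12/28 = 43%. Independent draws with six completers give 5:1 or worse in 14/64 = 22%.
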